Title of the study: Daily Weight Feedback for Wheelchair Users to Promote Weight Loss

NCT number: 03264248

Date: June 5th, 2018

[\[reviewer notes→\]](#)**Provide a short title for this study** (200 characters or less):**Daily weight feedback for wheelchair users to promote weight loss****T1.0****Select the type of application:**

New Research Study

T2.0**Is the proposed research study limited to the inclusion of deceased individuals?**

* No

T2.1**Are any research activities being conducted at the VA Pittsburgh Healthcare System or with VA funds?**

* No

[\[reviewer notes→\]](#)**T3.0****What is the anticipated risk to the research participants?**

Minimal Risk

T3.1**Why do you feel that all aspects of this research study, including screening and follow-up, involve no more than minimal risk to the research subjects?**

This study is a standard behavioral weight loss study focusing on diet, physical activity, and behavioral strategies to effectively make lifestyle changes. It will also include using a new scale (E-scale) which has minimal risk as it will continuously record the weight of the bed which will allow for capturing the weight of the person when they are in bed.

T4.0**Does the proposed study qualify for 'exempt' IRB review or for a determination of either 'not research' or 'no human subject' involvement?**

* No

T5.0**Does the proposed research study qualify for 'expedited' IRB review status?**

* Yes

[\[reviewer notes→\]](#)**CS1.0 What is the reason for this submission?**

New Research Protocol Submission

CS1.1**Has this research study been approved previously by the University of Pittsburgh IRB?**

* No

CS1.1.1**Has this research study (or a substantially similar research study) been previously disapproved by the University of Pittsburgh IRB or, to your knowledge, by any other IRB?**

* No

[\[reviewer notes→\]](#)**CS2.0****Title of Research Study:****Daily weight feedback for wheelchair users to promote weight loss****CS2.0.1****Requested approval letter wording:****CS2.1****Research Protocol Abstract:**

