To determine the usefulness, feasibility and efficacy of the E-scale system coupled with a standardized behavioral treatment weight-loss intervention for overweight or obese wheelchair users.

1.2 Specific Aims: List the goals of the proposed study (e.g., describe the relevant hypotheses or the specific problems or issues that will be addressed by the study).

Aim 1. To investigate the usefulness and feasibility of the E-scale system and efficacy of the E-scale coupled with a weight-loss intervention to assist overweight or obese wheelchair users with losing weight.

Hypothesis 1a: The E-scale will be useful based on self-reported feedback from wheelchair users by more than 50% stating that the E-scale is easy to use, their preferred weight monitoring system, them feeling that they would use the E-scale if it was available for them to purchase.

Hypothesis 2b: The E-scale will be feasible by providing accurate (+/- 2 lbs. from a calibrated scale measurement) and repeatable (<3lbs difference from day-to-day) weight measurements and by the wheelchair users continuing to use the scale more than 70% of the days of the study.

Hypothesis 2c: The E-scale coupled with the weight loss intervention will demonstrate efficacy by wheelchair users having significant improvements in weight, abdominal girth, body fat percentage and score on the Self-Rated Abilities for Health Practices Scale (SRAHP).

1.3 Background: Briefly describe previous findings or observations that provide the background leading to this proposal.

Wheelchair users have about twice the prevalence of obesity than the general population. There is also very little or no technology to which they have access to measure their weight frequently in their homes. Research however, has shown that monitoring your body weight frequently (i.e. daily) yields significantly better weight loss and weight maintenance results. This research has never included wheelchair users because they have not had access to technology to be able to measure their weight daily. The E-scale was developed as a weight monitoring technology for wheelchair users and has been tested for precision and accuracy in the laboratory.

1.4 Significance: Why is it important that this research be conducted? What gaps in existing information or knowledge is this research intended to fill?

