2.3 Summarize the general classification (e.g., descriptive, experimental) and methodological design (e.g., observational, cross-sectional, longitudinal, randomized, open-label single-blind, double-blind, placebo-controlled, active treatment controlled, parallel arm, cross-over arm) of the proposed research study, as applicable.

This study will be experimental. It will be a 13 week longitudinal efficacy study.

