After the subjects' have been determined to be eligible, they will have their abdominal girth measured with a tape measure and their body-fat percentage will be measured with a hand-held BIA inductance measuring tool. They will also be given a demographics questionnaire and the Self-Rated Abilities for Health Practices questionnaire to answer. The LoseIt! (diet and activity journal) and E-scale apps will be installed on their phones/android devices or they will be provided with an android device with the apps already installed to use during the study. De-identified login and passwords will be provided to the subjects to use during all of the study procedures so no identifiable data will ever be collected by these apps. Some training on use of the E-scale and LoseIt! apps will be provided to the subjects as well as the first lesson of the 13-week curriculum. Over the next few days, the study team will go to all of the subject's homes to install the E-scale under their beds.

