During the next 12 weeks, subjects will be asked to weigh themselves every day with the E-scale app and record their diet, exercise and weight every day with the LoseIt! app. The data that is reported in the LoseIt! app by the subjects will be monitored by the study team using the ascendapp for LoseIt!, which allows a "coach" to monitor all of the data submitted by a client. The weight loss curriculum involves weekly lessons for the participants to learn and practice things like counting calories and fat, reorganizing their kitchens, doing more cardio work around the house, etc. This curriculum was adapted from the Diabetes Prevention Program Group Lifestyle Balance (DPP GLB) curriculum at Pitt specifically for people with mobility impairments. The study team will send periodic emails with comments to the participants encouraging their progress and adherence to the protocol and lesson materials for that week. Every week at a pre-defined time, a group chat room will be conducted with all of the subject's and the research team invited to attend to go over the lesson for that week and to have a group discussion for the participants to share successes and difficulties with the group. The chat room will be hosted using Adobe Connect with the audio and video capabilities disabled. The link to the chat room for each week will be emailed to the subjects along with the lesson materials. The curriculum disbursement, progress emails, and chat rooms will be led by a dietitian/nutritionist with experience in leading group weight loss programs.

During the last week of the study (week 13). The subjects will be asked to come back to the lab in-person where their weight will again be measured using the roll-on scale. Their

abdominal girth and body-fat percentage will also be measured again. The SRAHP will be administered to the subjects again and they will also be given the final questionnaire, System Usability Scale (SUS), which will evaluate how they felt about the E-scale and some aspects of entire study. Any android devices that were loaned to the subjects during the study will be collected and the apps on their personal devices will be deleted if they wish. Over the next few days, the study team will visit all of the subject's homes to remove the E-scales or the participants can bring them with them to the lab.

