If a participant indicates during the study that the E-scale they are using is malfunctioning, an investigator may talk to the participant on the phone and/or schedule a time to travel to the subjects home to troubleshoot and/or replace the E-scale with one that is working properly.

2.6.1

Will blood samples be obtained as part of this research study?

* No

*If submitting a protocol for expedited review, it should be clear that the planned blood draws are within the parameters described here:

<http://www.hhs.gov/ohrp/policy/expedited98.html> (see Expedited Research Category #2)

If **Yes**, address the frequency, volume per withdrawal, the total volume per visit, and the qualifications of the individual performing the procedure:

Study Flow Chart:

Name Flowchart	Modified Date 4/17/2017 10:46 AM
--	-------------------------------------

[\[reviewer notes\]](#)

2.7

Will follow-up procedures be performed specifically for research purposes? Follow-up procedures may include phone calls, interviews, biomedical tests or other monitoring procedures.

* No

[\[reviewer notes\]](#)

2.8

Does this research study involve the use of any questionnaires, interview or survey instruments?

* Yes

Upload a copy of all materials except for the SCID or KSADS which are on file at the IRB. The use of all instruments must be addressed in question 2.6 and/or question 2.7 (except for an exempt submission where they should be addressed on the appropriate uploaded exempt form).

Name	Modified Date
EDDS	6/24/2017 2:48 PM
Screening tool	7/17/2017 4:35 PM
Final Survey	1/29/2018 9:45 AM
CES-D	6/24/2017 2:47 PM
Demographics	6/24/2017 2:50 PM
SRAHP	6/24/2017 2:50 PM

Previously the name and publisher for commercially available materials were listed in the textbox below but effective 9/1/2015, all materials (except for the SCID and KSADS) must be uploaded using the Add button above.

[\[reviewer notes→\]](#)

2.9

If subjects are also patients, will any clinical procedures that are being used for their conventional medical care also be used for research purposes?

* n/a

If **Yes**, describe the clinical procedures (and, if applicable, their frequency) that will be used for research purposes:

2.10 The blood sample question was moved to 2.6.1.

[\[reviewer notes→\]](#)

2.11 **What is the total duration of the subject's participation in this research study across all visits, including follow-up surveillance?**

* 13 weeks

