View	
Research Activity: Using E-scale
 
Common Risks: No Value Entered
 
Infrequent Risks: Breach of privacy with motion being detected. Height of the bed is increased by approximately 1/2 inch which could make transfers more difficult.
 
Other Risks: No Value Entered

5.1.1 **Describe the steps that will be taken to prevent or to minimize the severity of the potential risks:**

Consent, measurements and questionnaires: During all activities of consent, measurements and questionnaires we will provide the subjects will a private location to answer the questions. Subject codes will be used on all data collection forms. All identifiable information will be stored in a locked file room separate from the research data. The only linkage code will be stored on a password protected department server.

Installation and removal of E-scale: The study team will visit the participants' homes to install and remove the E-scale. It is possible that during this time, damage could be caused

to the participant's bed or surrounding areas. The investigator is liable for any damage that occur as a result of participation in the study and damage will be reimbursed accordingly. During the first visit, the investigator will assess the condition of the bed and items placed near the bedside. After such verification, it is to the discretion of the investigator if he wishes to continue with installation of E-Scale or disqualify the participant due to concerns with the bed. IRB # PRO14080007 is a past study using these scales with no adverse events.

Use of E-scale: During the use of the E-scale, the bed height will be raised by approximately 1/2 in when the sensors are under the bed legs. This may make transfers to and from bed more difficult for the wheelchair users. We will describe this risk during the consent process so they are aware and can withdraw from the study if they feel it will be an issue. The E-scale also collects the weight from the bed legs continuously and as such changes in weight distribution may make it possible to detect when the person is in or out of bed and if they are moving. We will also make the participants aware of this risk during the consent process.

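### Does Hypothesis 2b's 70% use criterion need rewriting because the study lasts 13 weeks but daily weighing is asked for over 12?

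*Combined protocol and SAP*

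**What the plan says.** Section 1.2, Hypothesis 2b, gives feasibility three parts: accuracy, repeatability and use. The use part is met "by the wheelchair users continuing to use the scale more than 70% of the days of the study".

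On the length of the study, section 2.3 says "It will be a 13 week longitudinal efficacy study". Item 2.11 asks "What is the total duration of the subject's participation in this research study across all visits, including follow-up surveillance", and the answer is 13 weeks.

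On the weighing schedule, section 2.6 first describes the baseline visit and then says "Over the next few days, the study team will go to all of the subject's homes to install the E-scale under their beds". It continues: "During the next 12 weeks, subjects will be asked to weigh themselves every day with the E-scale app". The final visit falls in week 13. The scale is collected in the days after that visit, or the participant brings it in.

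On what the device records, T3.1 says "it will continuously record the weight of the bed which will allow for capturing the weight of the person when they are in bed", and 5.1.1 says "The E-scale also collects the weight from the bed legs continuously".

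The criterion is not expressed in days anywhere. Section 2.18 plans mostly summary statistics, with paired t-tests for baseline against final measurements, and does not mention use. CS2.1 and 2.17 describe feasibility through accuracy and repeatability only.

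**The concern.** The denominator and the requested behaviour appear to cover different periods. If study days means all 13 weeks, seven days enter the denominator on which nobody was asked to weigh, and on some of them no scale was yet installed. A participant who did exactly what was asked, and nothing more, could not score 100%. One who weighed in on 70% to 75% of the requested days could be classed as a non-user.

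Two other gaps bear on the same criterion. A use day could be a weigh-in through the app or any night that the scale recorded passively. The 70% could be judged per participant, as a mean or on pooled days, whereas Hypothesis 1a states a share of users. Section 2.6 also foresees faults ("If a participant indicates during the study that the E-scale they are using is malfunctioning") without saying whether fault days count.

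At stake is one of the three parts of the feasibility verdict.

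**Working it through.** The plan has no derived figure to reproduce: 70% is a chosen threshold, given without a day count.

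**Inputs.** Study length is 13 weeks (2.3, 2.11), so 13 × 7 = 91 days. Requested weighing lasts 12 weeks (2.6), so 12 × 7 = 84 days. The threshold is strictly above 70% (1.2). The installation delay is a few days (2.6) with no number given; I assume 2 to 5.

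**1. The bar on each base.** The smallest whole number of days above 0.70 × base:

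| Base | 0.70 × base | Days needed | Share of the 84 days | Requested days that may be missed |
|---|---|---|---|---|
| 91 | 63.7 | 64 | 64/84 = 76.2% | 84 − 64 = 20 |
| 84 | 58.8 | 59 | 59/84 = 70.2% | 84 − 59 = 25 |

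The verdict differs only for someone with 59 to 63 use days (70.2% to 75.0% of the 84). For example, 63/84 = 75.0% passes and 63/91 = 69.2% does not. Using the scale on all 84 requested days and no others scores 84/91 = 92.3%.

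**2. What the 76.2% assumes.** It holds only if no use outside the 84 days counts. The hypothesis refers to using the scale, not to requested days. Each extra use day lowers the need within the 84 by one:

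- 1 extra day: 63/84 = 75.0%
- 5 extra days: 59/84 = 70.2%
- all 7: 57/84 = 67.9%

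**3. Installation delay.** If the 12 weeks start at baseline and 2 to 5 of the 84 days are lost, 64 days is 64/82 = 78.0% to 64/79 = 81.0% of what remains. The order of section 2.6 also allows another reading: baseline and installation fill week 1, and weighing runs over weeks 2 to 13. The delay then sits inside the seven days already excluded, and deducting it again would count it twice. On that reading 7 − 2 = 5 to 7 − 5 = 2 days of week 1 have a scale in place. If they are used and counted, the need within the 84 is 59 to 62 days (70.2% to 73.8%).

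**4. The analyst's likely choice: days with a scale installed.** Call baseline day 1, let installation take 2 to 5 days, and put the final visit on days 85 to 91. Installed days then run from 85 − 5 = 80 to 91 − 2 = 89. The bar is 57 days (0.70 × 80 = 56.0) to 63 days (0.70 × 89 = 62.3). By construction this is just over 70% of the days on which use was possible.

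**5. Group verdict (constructed examples).**

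- Twelve users with 63 days and three with 34: 12 of 15 exceed 70% on 84 days, and none on 91. This places all twelve at the top edge of a five-day window, so it is an extreme and not an expectation.
- Seven users with 84 days and eight with 42: pooled use is 924/1260 = 73.3% on 84 days and 924/1365 = 67.7% on 91. Judged per participant, 7 of 15 (46.7%) exceed 70% on either base (84/91 = 92.3%, 42/91 = 46.2%).

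**6. Use day.** A participant in bed every night who opens the app on 42 of 84 days scores 100% on passive recording and 50% on app weigh-ins. If passive recording counts, nights outside the 84 days count too, and neither the 76.2% nor the 92.3% ceiling holds. The denominator complaint therefore needs the app-only definition, which the text does not fix.

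**The case for a change.** The best case for a change is that three choices (base, use day and unit of judgement) are all open, so the use verdict could be picked after the data are seen. The use-day gap alone can move one person from 50% to 100%, far more than the five-day question. A few dated lines would close all of it.

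It is true that none of the three is written down, and that the documents do not say whether app weigh-ins are logged apart from the continuous recording. It is also true that a 91-day base counts some days without a scale as non-use.

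The step from there to a faulty criterion does not stand. Continued use presupposes an installed scale, so a base of weighing days or installed days is a natural reading. Section 2.6 describes the requested act as weighing through the app, and section 1.4 bases the study's value on people monitoring their weight daily, so an app weigh-in is the sensible meaning of a use day. The remedy would let the sponsor keep 91 days or choose another base. It would record a choice and correct no number.

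**Conclusion.** The concern does not call for a change. The 13-week and 12-week periods are both in the text and the arithmetic is right: 64 days against 59, a difference of five per participant. The statement that the criterion demands 76.2% of requested days rests on two readings that the plan does not impose: that the base is 91 days, and that use outside the 84 days is ignored. Relaxing the second alone takes the figure from 76.2% down to as little as 67.9%.

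What remains is missing detail in a feasibility benchmark. Section 3.12 reports that no sample size calculation was made, no test or error rate uses the 70%, and section 2.18 relies mainly on summary statistics for a single group of up to 15. An analyst would sensibly count days with a scale installed. Once use days are reported, any reader can restate them over 84 or 91 days. The conclusion assumes that use is reported as day counts and not only as a pass or fail. The 2-to-5-day delay and the splits of 15 are illustrations, not figures from the plan.

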The goals of the proposed study are to test the usability, feasibility and preliminary efficacy of the E-Scale with wheelchair users. Up to fifteen overweight or obese wheelchair users will be enrolled in a 13 week study that includes standard behavioral treatment (SBT) for weight loss that focuses on diet, physical activity, and behavioral strategies (e.g., goal setting, self-monitoring) to support lifestyle changes specifically for people with mobility impairments. The subjects will also be provided the E-scale to track their weight daily. The primary outcomes will be usefulness (subjective feedback from a survey about the program/E-scale), feasibility (accuracy and repeatable measurements from the E-scale) and efficacy (improvements in weight and other measures of health) of the weight loss program coupled with the E-scale at the end of 13 weeks. The results could inform the refinement of this technology to increase its applicability for wheelchair users to independently monitor their weight in their own homes while attempting to lose weight.

CS2.2**Select the category that best describes your research:**

Hybrid - includes aspects of BOTH types of research (check this option if your research is mainly social/behavioral but also involves specimen collection or blood draws to look at biological measures)

[\[reviewer notes→\]](#)**CS3.0 Name of the Principal Investigator:**

Note: Adjunct faculty of the University, including lecturers and instructors, are not permitted to serve as a PI or Faculty Mentor but may serve as co-investigators. Refer to [Chapter 4](#) on the HRPO website for more information.

CS3.1 Affiliation of Principal Investigator:

UPitt faculty member

If you chose any of the **Pitt options**, please indicate the specific campus:

[Main Campus - Pittsburgh](#)

If you chose the UPitt faculty member option, provide the PI's **University Faculty Title**:

Associate Professor

CS3.2 Address of Principal Investigator:

[name]
[name]

CS3.3 Recorded Primary Affiliation of the Principal Investigator:

U of Pgh | School of Health and Rehabilitation Sciences | Rehabilitation Science and Technology

CS3.4 Identify the School, Department, Division or Center which is responsible for oversight of this research study:

[U of Pgh | School of Health and Rehabilitation Sciences](#)

CS3.5 Telephone Number of Principal Investigator:

[contact]

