[\[reviewer notes→\]](#)

2.12 **Does this research study involve any type of planned deception?**

If Yes, you are required to request an alteration of the informed consent process (question 4.7)

* No

[\[reviewer notes→\]](#)

2.13 **Does this research study involve the use of UPMC/Pitt protected health information that will be de-identified by an IRB approved "honest broker" system?**

* No

[\[reviewer notes→\]](#)

2.14

Will protected health information from a UPMC/Pitt HIPAA covered entity be accessed for research purposes or will research data be placed in the UPMC/Pitt medical record?

* No

2.14.1

Will protected health information from a non-UPMC/Pitt HIPAA covered entity be obtained for research purposes or will research data be placed in the non-UPMC/Pitt medical record?

* No

[\[reviewer notes→\]](#)

2.15

Does this research study involve the long-term storage (banking) of biological specimens?

* No

[\[reviewer notes→\]](#)

2.16

Will research participants be asked to provide information about their family members or acquaintances?

* No

[\[reviewer notes→\]](#)

2.17

What are the main outcome variables that will be evaluated in this study?

Subjective feedback from the survey about the usefulness and participants' satisfaction with portions of the program and E-scale.

Accuracy and repeatability of the E-scale measurements

Weight change, abdominal girth change, body-fat percentage change and Self-Rated Abilities for Health Practices (SRAHP) change

2.18

Describe the statistical approaches that will be used to analyze the study data.

* Addressed below:

Since there is only one group, most outcome variables will be analyzed using summary statistics. Baseline and final measurements will also be analyzed using paired t-tests.

[\[reviewer notes→\]](#)

2.19

Will this research be conducted in (a) a foreign country and/or (b) at a site (e.g., Navajo Nation) where the cultural background of the subject population differs

substantially from that of Pittsburgh and its surrounding communities?

- * No

Note that copies of training records, licenses, certificates should be maintained in the study regulatory binder and are subject to audit by the Research Conduct and Compliance Office (RCCO).

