3.8 Does this research study involve neonates of uncertain viability or nonviable neonates?

- * No

[\[reviewer notes→\]](#)

3.9 Fetal Tissues: Does this research involve the use of fetal tissues or organs?

- * No

[\[reviewer notes→\]](#)

--->

3.10 What is the total number of subjects to be studied at this site, including subjects to be screened for eligibility?

Note: The number below is calculated by summing the data entered in question 3.11. Any additions or changes to the values entered in 3.11 will be reflected in 3.10.

- * 20

3.11

Identify each of the disease or condition specific subgroups (include healthy volunteers, if applicable) that will be studied.

Click on the "Add" button and specify for each subgroup:

- 1) how many subjects will undergo research related procedures at this site; and**
- 2) if applicable, how many subjects will be required to undergo screening procedures (e.g., blood work, EKG, x-rays, etc.) to establish eligibility. Do Not include subjects who will undergo preliminary telephone screening.**

*

Subgroup	Number to undergo research procedures	Number to undergo screening procedures
All subjects	15	20

3.12 Provide a statistical justification for the total number of subjects to be enrolled into this research study at the multicenter sites or this site.

- * Described below:

Since this is an efficacy and exploratory study no sample size calculation was needed or conducted. Similar weight loss studies include 10-20 people in each group session or cohort.

[\[reviewer notes→\]](#)

3.13 Inclusion Criteria: List the specific criteria for inclusion of potential subjects.

- Use Wheelchair as primary means of mobility
- Uses a bed with 4 legs
- BMI ≥ 27 and ≤ 40.0
- age 18-80
- Has daily access to Internet to access LoseIt website and/or app and weekly chat meeting (Adobe Connect)
- Currently owns or willing to use an android device
- Provides physician's clearance to participate in a weight loss intervention
- Speaks English

3.14 Exclusion Criteria: List the specific criteria for exclusion of potential subjects from participation.

- Presence of an unstable condition requiring physician-supervised diet and exercise (e.g., diabetes, recent myocardial infarction)
- Presence of condition precluding engagement in exercise at moderate intensity (e.g., asthma, congestive heart failure, etc.)
- Pregnancy or intention to become pregnant during study

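### Hypothesis 2c lets significant pre-post change in one uncontrolled group of at most 15 people count as demonstrated efficacy, which the design cannot show

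*Combined protocol and SAP*

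**What the plan says.** Section 1.2, Hypothesis 2c, sets the efficacy criterion: the E-scale coupled with the programme "will demonstrate efficacy by wheelchair users having significant improvements in weight, abdominal girth, body fat percentage", and the sentence goes on to add the SRAHP score as a fourth outcome. The four are joined by a plain conjunction. No significance level, sidedness or rule for combining the four is stated.

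Section 2.18 gives the whole analysis plan in two sentences: "Since there is only one group, most outcome variables will be analyzed using summary statistics", and "Baseline and final measurements will also be analyzed using paired t-tests". It names no confidence interval or other measure of precision for the change.

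The documents do not agree on the status of the study:

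- The abstract (CS2.1): the goals are to "test the usability, feasibility and preliminary efficacy of the E-Scale with wheelchair users", and "Up to fifteen overweight or obese wheelchair users will be enrolled in a 13 week study".
- Section 3.12: "Since this is an efficacy and exploratory study no sample size calculation was needed or conducted".
- Section 2.3: "It will be a 13 week longitudinal efficacy study".
- Section 1.1 states the purpose as determining efficacy, with no qualifier.
- Section 1.4 says the research will also show whether wheelchair users do better on weight loss when they monitor their weight daily.

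**The concern.** Hypotheses 1a and 2b set pass criteria for usefulness and feasibility, and 2c does the same for efficacy. It is the only efficacy criterion in the plan, and it is a significance verdict. The study that has to carry that verdict has one arm, gives everyone the scale and the programme together, enrols at most 15, and is described in its own abstract as preliminary.

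If the plan is followed as written, the report will say that efficacy was, or was not, demonstrated. Neither statement follows from the data. The first attributes a before-and-after change to the package without a comparator. The second treats an imprecise estimate as a negative finding. The abstract says the results could inform refinement of the technology. An estimate with its uncertainty serves that purpose better than a verdict.

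**Working it through.** **Inputs from the documents.** One group (2.18). Paired t-test, baseline against week 13 (2.18, 2.6). Maximum of 15 participants (CS2.1, 3.11). Four outcomes (1.2). No effect size, SD, significance level or dropout rate is given, so the plan has no figure of its own to reproduce.

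**Assumptions.** Two-sided 5%. Completers ranging from 15 down to 8, because 15 is a ceiling and section 5.7 removes people after two weeks without participation or more than five days in hospital. Changes are expressed in units of the SD of change.

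**Step 1: what a significant result would mean.** The paired t-test addresses whether the mean change is zero. The observed change combines any effect of the scale, any effect of the programme, the effect of being in a study, regression to the mean, and drift. Suppose the E-scale adds nothing and the other sources together produce a change of 0.8 SD. The test is then significant 82% of the time at n = 15; at 1.0 SD it is 95%. The test works correctly in that case, but its result says nothing about cause, and nothing about the scale separately from the programme.

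**Step 2: precision.** Half-width of the 95% interval for the mean change = t(0.975, n−1) / √n, in SD units.

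| Completers | t(0.975, n−1) | Half-width (SD) |
|---|---|---|
| 15 | 2.145 | 2.145/√15 = 0.554 |
| 12 | 2.201 | 2.201/√12 = 0.635 |
| 10 | 2.262 | 2.262/√10 = 0.715 |
| 8 | 2.365 | 2.365/√8 = 0.836 |

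The same figure is the smallest observed mean change that reaches significance. For scale only: if the SD of weight change were 5 to 8 lb (an assumption), the half-width at n = 15 would be 0.554 × 5 = 2.8 lb to 0.554 × 8 = 4.4 lb, and at n = 10 it would be 3.6 to 5.7 lb.

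**Step 3: what a non-significant result would mean.** Power of a single paired t-test (noncentral t):

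| True change (SD) | n = 15 | n = 12 | n = 10 |
|---|---|---|---|
| 0.3 | 19% | 16% | 14% |
| 0.5 | 44% | 35% | 29% |
| 0.8 | 82% | 71% | 62% |
| 1.0 | 95% | 88% | 80% |

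The test detects large changes and often misses moderate ones.

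**Step 4: four outcomes.** By simulation, with equal correlation between outcomes from 0 to 0.8 and counting improvements only:

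- Requiring all four to be significant at n = 15, with a true change of 0.8 SD on each, succeeds 46% to 68% of the time. At n = 10 it is 15% to 41%. With no true change it succeeds at most about 0.5% of the time.
- If any one were enough, the chance of at least one significant improvement with no true change would be 6% to 10%.

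The natural reading of 2c is all four. On that reading a false claim of change is rare, but a failure to demonstrate is common even when every outcome has truly improved by 0.8 SD.

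**The case against.** Several points on the other side are sound.

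- **A paired t-test is valid at n = 15.** The absence of a sample size calculation does not invalidate it or inflate its error rate. A reader might infer from section 3.12 that the test may not be used at all; the documents do not support that. The problem is the conclusion attached to the test.
- **The rule covers four outcomes.** A reader might infer that a weight loss of about 3 to 4 lb alone would count as demonstrated efficacy. Read literally, 2c also needs girth, body fat and SRAHP to improve significantly.
- **The test is not uninformative about weight.** A reader might infer that it says little in either direction, or that it would miss a 5% loss. At an assumed height of 66 in, BMI 27 is 27 × 66²/703 = 167 lb, and 5% of that is 8.4 lb. With the larger assumed SD of 8 lb this is 8.4/8 = 1.05 SD, where power is about 96% at n = 15 and 84% at n = 10. Nor can 2.8 to 4.4 lb (0.554 SD) be dismissed as trivial while 2.5 to 4.0 lb (0.5 SD) is called a moderate loss; they are nearly the same change.
- **The 5% in section 3.14 is not an efficacy benchmark.** It excludes people who have lost that much in the past six months.
- **The plan is not confined to p-values.** Section 2.18 puts summary statistics first and adds the t-tests. The abstract describes efficacy as improvement, without a significance condition, and no go/no-go decision is tied to 2c.

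These points limit the concern but do not remove it. Section 2.18 promises no interval, 2c still makes significance the route to efficacy, and nothing in the design supplies a comparator.

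**Conclusion.** The concern holds in this form: the conclusion that 2c allows is stronger than the design supports, and the wording conflicts with the abstract. The main reason is the missing control group, which needs no numerical assumption. Imprecision is the second reason: an interval of about ±0.55 SD of change with 15 completers and ±0.72 SD with 10, assuming a two-sided 5% level. A non-significant result therefore leaves room for a useful change, and more so if all four outcomes must succeed together.

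The statement in section 1.4 about daily weighing overreaches further, since everyone is asked to weigh daily and there is no group that does not.

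This should be changed, but it is a matter of wording and reporting. The planned measurements and the t-test itself can stand.

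**What to change.** 1. **Section 1.2, Hypothesis 2c:** replace the efficacy verdict with an estimation aim, for example: we will estimate the change from baseline to week 13 in weight, abdominal girth, body-fat percentage and SRAHP as preliminary, uncontrolled evidence. Remove significance as the rule that demonstrates efficacy.
2. **Section 2.18:** report each mean paired change with its 95% confidence interval and the number of participants contributing. Label any p-values supportive, with the level and sidedness stated. Say that a non-significant result is not evidence of no change.
3. **Sections 1.1 and 2.3:** qualify efficacy as preliminary, matching the abstract.
4. **Section 1.4:** withdraw the statement that the study will show better outcomes with daily weighing, or recast it as a question for a later controlled study.
5. **Optional:** a count of participants losing at least 5% of baseline weight, as description only, since section 3.14 uses that figure for exclusion.

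The cost is a few sentences of text and intervals computed from data already planned, with no added participants or visits. The sponsor gives up a yes/no efficacy claim.
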